4.2. Definitions/derived variables

Unless otherwise specified, baseline is defined as value collected closest but not later than time of the first IMP administration (Day 1 Baseline).

As most of the procedures on Day 1 Baseline are performed before IMP administration, values for following forms will be used as baseline:

- TJC/SJC/DAS-28 CRP on Day 1 Baseline,
- Patient Assessment of Arthritis Pain (PAAP) on Day 1 Baseline,
- Patient's Global Assessment of Arthritis (PtGA) on Day 1 Baseline,
- Physician Global Assessment of Arthritis (PhGA) on Day 1 Baseline,
- Health Assessment Questionnaire – Disability Index (HAQ-DI) on Day 1 Baseline,
- Functional Assessment of Chronic Illness Therapy – Fatigue (FACIT-F) on Day 1 Baseline,
- 36-Item Short Form Survey Instrument (SF-36) on Day 1 Baseline,
- Vital signs on Day 1 Baseline,
- Clinical laboratory data (hematology, biochemistry, urinalysis, lipid profile, coagulation profile, rheumatoid biomarkers indicators) on Day 1 Baseline,
- 12-lead ECG on Day 1 Baseline,
- PK blood sample collection [predose] on Day 1 Baseline,

4.2.1. Day 1 and relative study days

Day 1 is defined as the day of the first administration of study medication (reference date). In general, any date provided in patient listings will be presented as study day (in addition to the date provided): If a date is later than the reference date then the study day is calculated as:

$$\text{study day} = \text{date} - \text{reference date} + 1.$$

If a date is prior the reference date then the study day is a negative number calculated as

$$\text{day} = \text{date} - \text{reference date}.$$

No study day 0 will exist.

4.2.2. BMI

BMI is calculated according to the equation:

$$\text{BMI} = \text{weight [kg]} / \text{height [m]}^2$$

BMI will be subsequently categorized using following ranges:

<18.5 – Underweight

<18.5 – 25) – Normal weight

<25 – 30) – Overweight

≥30 – Obese.

4.2.3. Amount of cigarettes smoked – pack-years

It is assumed that pack of cigarettes contains 20 items.

Number of cigarettes per day will be calculated following conversion table.

Table 3. Conversion to number of cigarettes smoked per day

Unit	Frequency	Multiplier
Cigarettes	Daily	1
	Every week	0.1429
	Every month	0.0329
	Per year	0.0024
Packs	Daily	20
	Every week	2.8571
	Every month	0.6571
	Per year	0.0548

Note: Length of year – 365.25 days, length of month – 30.4375 days.

If start or end date of smoking is missing or partially missing the imputation of dates described in section 4.6 will be used.

Duration of smoking will be calculated as follows:

If former smoker:

Duration in years = (End date of smoking - Start day of smoking)/365.25.

If current smoker:

Duration in years = (Date of screening visit - Start day of smoking)/365.25.

Pack years will be calculated as follows:

Number of pack-years = (number of cigarettes smoked per day/20) * number of years smoked.

4.2.4. Duration of rheumatoid arthritis

Duration of rheumatoid arthritis will be calculated as:

Duration of rheumatoid arthritis = (date of signature of ICF – date of rheumatoid arthritis diagnosis)/365.25,

where ICF is Informed Consent Form.

For partial dates imputation described in section 4.6 will be used prior to duration calculation.

4.2.5. Duration of methotrexate treatment

Duration of methotrexate treatment will be calculated as:

Duration of methotrexate treatment = (date of signature of ICF – start date of methotrexate treatment)/365.25,

where ICF is Informed Consent Form.

For partial dates imputation described in section 4.6 will be used prior to duration calculation.

4.2.6. Treatment exposure and treatment compliance

Drug exposure is the total number of days the patient takes study drug during the overall study period (not including interruptions). Exposure to IMP will be calculated as:

Exposure = (Last IMP dose – First IMP dose) + 1 - sum of interruptions

Extent of exposure will be calculated as a sum of exposures of all patients and expressed in patient-treatment years:

Extent of exposure [patient months] = sum(Exposure)/30.44.

Drug adherence will be assessed based on patient's diary and calculated as:

Drug adherence [%] = Number of compliant doses taken/Number of doses to be taken
100%*

A single dose is to be consider as a compliant when all 4 tablets are administered. Number of doses to be taken is equal to 169 (84 days * 2 + 1).

A patients is to be considered as a complier with dosing regimen when at least 80% of the doses are compliant (136 doses).

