## **6.6. Dosing**

All tablets are to be administered orally. CPL409116 tablets should be taken under fasted conditions (after a minimum 6 hours overnight fast in the morning minimally, 2 hours after the last food consumption in the evening and 2 hours prior to the next meal consumption in the evening), but preferably should be taken consistently in the same manner and at the same time each day. Exceptionally on study visit days patients will be instructed to refrain from dosing at home, and will take the study medication at the clinic. Subjects should swallow the tablets with water to a total volume of approximately 250 mL. It is important that subjects swallow the investigational product whole, and that they not manipulate or chew the investigational product prior to swallowing. Sites will instruct subjects on the proper way to remove tablets from blister packs and how subjects will administer the IMP at home. Subjects will be instructed to self-administer their study medication according to administration instructions provided to the subject. Subjects will be instructed not to remove tablets from the blister packaging until the time of dosing. Patients will be given a subject diary and provided with instructions on the completion of the diary. The diary won't be filled during Patient's visit at Site. The data during ambulatory visits will be recorded in source documentation.

In this phase of the proof of concept clinical trial patients are to take tablets containing 60 mg of IMP (Table 3).

Table 3. The number of tablets for each potential dose of CPL 409116 for the study.

PG24 DOSE	NUMBER OF TABLETS (60 mg)
60 mg	1
120 mg	2
240 mg	4

Patients are to be randomized to one of four study arms with assigned appropriate dose of CPL409116: 60 mg (study arm 1); 120mg (study arm 2) or 240 mg (study arm 3) administered twice a day and with assigned placebo (study arm 4). Every patient included in the study and randomized is to take the same number of

tablets (4 tablets) in the morning and in the evening to blind substances which are to be taken by participants. This number of tablets (4 tablets per administration) is to be corresponding to the highest possible dose of CPL409116 equals 240 mg per administration (4 tablets). The table below shows the number of tablets which are to be taken by participants in particular arms of the study.

Table 4. The number of tablets administered by patients depending on the study arm.

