## 6.7. Compliance and IMP Accountability

Dosing will be performed by trained and qualified personnel designated by the Investigator during the ambulatory visits in the morning. The date and time of IMP dosing will be documented on each dosing day during the outpatient visits. During home dosing periods (including evening dosage), time of IMP and methotrexate dosing should be documented in the patient's Diary. Comments will be recorded if there are any deviations from the planned dosing procedures. A single dose is to be consider as a compliant when all 4 tablets are administered, and administration is without any emesis occurring within 2 hours after IMP administration. A patient is to be considered as a complier with dosing regimen when at least 80 % of the doses are compliant (at least 136 doses). Compliance from days of home dosing will be verified by a designated person taking into account data from the Patient's diary and empty blisters patient brings on the next visit and during phone call visits. On Day 85 subjects will be hospitalized up to Day 86 in the morning due to donation of blood samples for PK analysis in 13 timepoints. Subjects can spend Day 85 night to Day 86 outside of the clinic but it is necessary to return on Day 86 in the morning in order to donate the last sample of blood 24h after morning CPL409116 administration on Day 85. The Sponsor shall supply an adequate quantity of the investigational medicinal product (IMP) and the placebo, both for administration and as a backup, along with the respective certificates of analysis (CoA). The amount of each product should be sufficient to account for any loss resulting from its potential damage or subject's withdrawal.

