**Administration of IMP/ placebo and next:**

- Collect blood samples to the PK analysis 0.5; 1.0; 1.5; 2.0; 2.5; 3.0; 4.0 and 6.0h (+/- 5 min) after CPL409116 administration;
- 
- Dispense investigational product/ placebo;
- Dispense a diary part to subject and instruct subject on proper use of the diary;
- Dispense of Patient's card
- Adverse events monitoring.

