All patients will undergo PK sampling during the Treatment Period. Timepoints are indicated on the basis of PK results from PART B of the study 01JAK2020. Blood samples collection for PK analysis will take place on Day 1/ Baseline; 8; 29; 57 and 85/86. Blood samples for PK analysis are to be collected on the following time points: on Days 1, 8, and 57 at timepoints: pre-dose and 0.5, 1.0, 1.5, 2.0, 2.5, 3.0, 4.0, and 6.0h after CPL409116 administration in the morning; and on Day 29 at timepoints: pre-dose (0.0) and 2.5h after CPL409116 administration in the morning. On Day 85 PK blood sample collection is to be carried out in 13 timepoints, as follows: pre-dose (0.0) and 0.5, 1.0, 1.5, 2.0, 2.5, 3.0, 4.0, 6.0, 8.0, 10, 12, and 24h (Day 86) after CPL409116 administration in the morning.

Investigational product tablets will be administered to the subject in the clinic on the morning of clinic visits and all other dosing will be performed by the subject outside the clinic, at home. Additionally, apart from ambulatory visits which take place on Day 1/ Baseline; 8; 29; 57 and 85, on Day 43 (Week 6) and on Day 71 (Week 10) phone call to patients will be made to monitor potential adverse events and compliance check.

[figure not shown]

Figure 3. Scheme of 12-week treatment period

Between ambulatory visits subjects are to administer investigational medicinal product outside the clinic, at home. During the Day1/ Baseline subject diary and appropriate number of tablets with active substance or placebo will be dispensed in a clinical site. Subjects are to be obligated to complete the diary every time after investigational product administration (in the morning and in the evening). The diary is to be verified during ambulatory visits on the following Days: 8, 29, 57 and 85 to IMP accountability and compliance check. At every outpatient visit appropriate number of CPL409116/placebo tablets and a new part of the Patient's diary will be dispensed whereas the previous part of diary (completed) is to be attached to the documentation of the study. The last part of the Patient's diary is to be dispensed on Day 57 (Week 8) and collected on Day 85 (Week 12). If required patients will be retrained during ambulatory visits. Subjects are to be obligated to hand empty aluminum blisters back to a clinical unit.

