aa. Blood samples for PK analysis are to be collected on the following Days: 1/Baseline; 8; 57 (timepoints: pre-dose (\leq 5 minutes prior to CPL409116 administration); 0.5h; 1.0h; 1.5h; 2.0h; 2.5h; 3.0h; 4.0h; 6.0h after CPL409116 administration) and on Day 29 in the following timepoints: pre-dose (\leq 5 minutes prior to CPL409116 administration) and 2.5h after CPL409116 administration. On Day 85 PK blood sample collection is to be carried out in 13 timepoints, as follows: pre-dose (\leq 5 minutes prior to CPL409116 administration); 0.5h; 1.0h; 1.5h; 2.0h; 2.5h; 3.0h; 4.0h; 6.0h; 8.0h; 10h; 12h and 24h after morning CPL409116 administration on Day 85.

cc. Effectiveness assessment will be performed by using clinical scales. Patients as well as Investigators will be engaged in filling out the questionnaires. Patient reported assessments, including PtGA and PAAP VAS measures and HAQ-DI questionnaires, should be performed prior to any other assessments. Questionnaires designed for patients should be filled out before the patient contact with medical staff and Investigator of a clinical unit. Additional unscheduled assessments should be performed as clinically indicated. Tender/Painful Joint Count (68) and Swollen Joint Count (66) will be performed at Screening; Day 1/baseline; Day 29;57; 85; 113 and in case of early withdrawal. DAS28-CRP will be performed at Screening; Day 1/Baseline; Day 29; 57; 85; 113 and in case of early withdrawal. FACIT-F (Fatigue) and SF-36 RAND will be performed on Day 1/baseline; Day 85;113 and in case of early withdrawal. On study drug dosing days, assessments (including joint counts and questionnaires), and pre-dose blood collections are to be performed prior to dosing unless otherwise stated.

dd. Investigational product tablets will be administered to the subject in the clinic on the morning of clinic visits and all other dosing will be performed by the subject outside of the clinic. The last dose of CPL409116 will be administered on Day 85 in the morning. Nightly CPL409116 dose on Day 85 is to be skipped.

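### SAP 4.2.6 counts adherence from the patient's diary over 169 doses, five of which are given in the clinic and, under Protocol 6.6, are not entered in the diary

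*SAP*

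**What the plan says.** **Numerator and denominator.** SAP 4.2.6 states: "Drug adherence will be assessed based on patient's diary and calculated as" the number of compliant doses taken, divided by the number of doses to be taken. For the latter: "Number of doses to be taken is equal to 169 (84 days * 2 + 1". The complier rule follows: "A patients is to be considered as a complier with dosing regimen when at least 80% of the doses are compliant (136 doses". Protocol 6.7 sets the same limit: "when at least 80 % of the doses are compliant (at least 136 doses".

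**Clinic doses.** SAP 2.2 lists the treatment-period visits: "apart from ambulatory visits which take place on Day 1/ Baseline; 8; 29; 57 and 85". The footnotes to the schedule in SAP 2.2.3 say where the visit-day morning dose is taken: "Investigational product tablets will be administered to the subject in the clinic on the morning of clinic visits". The Day 85 morning dose is the last; the evening dose that day is skipped.

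**What goes in the diary.** Protocol 6.6 says: "The diary won't be filled during Patient's visit at Site. The data during ambulatory visits will be recorded in source documentation". Protocol 6.7 likewise splits the record. Staff document the date and time of dosing at outpatient visits, and the diary covers home dosing, including evening doses. At Visit 2, Protocol 9.2 lists this step among those that follow the clinic dose: "Dispense a diary part to subject and instruct subject on proper use of the diary".

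**Text that points the other way.** Protocol 4.1, repeated in SAP 2.2, obliges subjects to complete the diary after each administration, morning and evening. That sentence stands in a paragraph that opens with dosing at home between visits.

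**Use.** SAP 4.17 presents adherence and compliance in tables of descriptive statistics.

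**The concern.** The numerator and the denominator of the adherence percentage do not cover the same doses. The protocol builds its 136-dose limit on two records: the diary for home doses and staff documentation for clinic doses. SAP 4.2.6 keeps the full 169-dose basis and the 136-dose limit but names only the diary. It neither adds the clinic doses to the numerator nor removes them from the denominator.

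At stake is whether the reported adherence figures are right. Read literally, the rule makes 100% unattainable for a patient who took every dose, pushes adherence down in every arm, and makes the complier label stricter than the 80% that both documents state.

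**Working it through.** **Inputs.** Denominator 169 and limit 136 (SAP 4.2.6; limit also in Protocol 6.7). Five clinic morning doses, on Days 1, 8, 29, 57 and 85 (SAP 2.2 and 2.2.3). Clinic doses not entered in the diary (Protocol 6.6).

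**Step 1: reproduce the plan's figures.** 84 × 2 + 1 = 169. 0.80 × 169 = 135.2, so the smallest whole number that reaches 80% is 136 (136/169 = 80.5%; 135/169 = 79.9%). Both stated figures are correct.

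**Step 2: count the doses the diary can hold.** Mornings at home: 85 − 5 = 80. Evenings at home: 84, since the Day 85 evening dose is skipped. Total 80 + 84 = 164 = 169 − 5.

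**Step 3: ceiling and shortfall.** A patient who takes every dose scores 164/169 = 97.0%. The shortfall is 5/169 = 3.0 percentage points when all five clinic doses are compliant, and less if fewer are.

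**Step 4: effective cut-off.** Reaching 136 from the diary alone needs 136/164 = 82.9% of home doses. The patient may miss 164 − 136 = 28 doses, where the stated rule allows 169 − 136 = 33.

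**Step 5: who would be mislabelled.** With all five clinic doses compliant, a true total T appears in the diary as T − 5. The label is wrong when T ≥ 136 but T − 5 < 136, that is, for T from 136 to 140.

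| True total | True adherence | Diary total | Scored adherence |
|---|---|---|---|
| 136 | 80.5% | 131 | 77.5% |
| 137 | 81.1% | 132 | 78.1% |
| 138 | 81.7% | 133 | 78.7% |
| 139 | 82.2% | 134 | 79.3% |
| 140 | 82.8% | 135 | 79.9% |

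**Step 6: how often, under an assumption.** The documents give no expected adherence. As an illustration only, suppose every home dose is compliant independently with the same probability p, and all five clinic doses are compliant. The mislabelled share is then P(131 ≤ X ≤ 135) with X binomial (164, p).

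| Assumed p | Share mislabelled |
|---|---|
| 0.75 | 7.6% |
| 0.78 | 24.5% |
| 0.80 | 36.0% |
| 0.82 | 36.7% |
| 0.85 | 16.5% |
| 0.90 | 0.2% |
| 0.95 | about 0% |

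Real patients differ from one another and miss doses in runs, so these shares show only where the risk lies: close to the 80% limit.

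**Step 7: the two possible repairs.** Adding the clinic doses to the numerator gives a perfect patient 169/169 = 100%, leaves the cut-off at 136, and mislabels nobody in the band above. Restricting the measure to home doses gives 164/164 = 100%, but 0.80 × 164 = 131.2, so the cut-off becomes 132 and the 136 in both documents would have to change.

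**The case against.** **The diary may contain the clinic doses.** A reader might infer that clinic doses are never written there. The documents do not settle it so flatly, because Protocol 4.1 and SAP 2.2 call for an entry after each administration. Protocol 6.6 is the better guide, since it deals specifically with visits, while the other sentence sits among text on home dosing. The two still conflict on their face and need reconciling.

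**The SAP plainly means clinic doses to count.** The numerator is worded as doses taken, not doses written in the diary, and the final +1 in the 169 is itself the Day 85 clinic dose. Visit dosing times are documented, and Protocol 10.5 and 10.6 plan to list administration dates and times. A programmer who found five staff-given doses missing for every patient could well fill them in. This is fair as a guess at intent. But SAP section 1 says the document covers all aspects of the analysis, and 4.2.6 gives no instruction to use a second source.

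**The consequence is small.** This largely stands. Three stronger readings are tempting and not supported:

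- *That true compliers will be mislabelled.* This needs patients with true totals of 136 to 140, and nothing in the documents says there will be any.
- *That the per-protocol set is distorted.* The dosing criterion in SAP 3.3 concerns a substantial departure from the dosing schedule. It cites neither 80%, nor 136 doses, nor the adherence formula, and deviations are classified at a data review before unblinding. The adherence figure could inform that review, but the text makes no such link.
- *That the comparison between arms is biased.* The visit schedule is the same in every arm, so the understatement has no direct route to a treatment contrast.

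**Conclusion.** The mismatch is real and minor. Applied as written, SAP 4.2.6 understates adherence for completers by up to 3.0 percentage points, with a ceiling of 97.0%, and raises the working limit from 80% of all doses to 82.9% of home doses. Patients with all five clinic doses compliant and a true total of 136 to 140 doses would be labelled non-compliers. Whether there are any depends on the data; at about 90% adherence or higher there would be almost none.

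This rests on two assumptions: that Protocol 6.6 governs visit days, and that the diary is the only source used. The effect reaches the descriptive adherence and complier summary only. The primary ITT analysis does not use it, and complier status defines no analysis set or endpoint.

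**What to change.** In SAP 4.2.6, define compliant doses as compliant home doses recorded in the diary plus compliant clinic doses from the visit dosing record (source documentation, or the drug-administration data to be listed under Protocol 10.5 and 10.6). Keep 169 and 136 for patients who complete Day 85, so that both documents retain their stated figures.

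Reconcile the sentence in Protocol 4.1 and SAP 2.2 on completing the diary after each administration with Protocol 6.6, so that it is clear which doses the diary holds.

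The cost is one sentence in the SAP and one clarification. Clinic dosing times are already documented under Protocol 6.7, so no new data are collected. The sponsor should confirm that they are held in the database: Protocol 6.6 mentions only source documentation, and the planned listings make database capture likely without showing it.

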**NOTE:** Randomisation will take place at the end of the Screening period when it is confirmed by an Investigator that a participant fulfilled all inclusion criteria and none of exclusion criteria available at the time of randomisation (pre-final confirmation). Patients will be randomised at the end of the screening period (1-2 days before Day1/ Baseline) in order to generate the randomisation code which is necessary to prepare appropriate number of IMP/ placebo for a patient. Pre- final conformation will take place after the negative result of COVID-19 test is received. The rest of inclusion and exclusion criteria unavailable at Screening will be verified on Day1/ Baseline (final conformation). The final conformation will take place before the first dose of IMP/placebo administration on Day1/ Baseline.

After randomization and during the **Treatment Period**, patients are to be dosed with 60, 120 or 240 mg CPL409116 administered twice a day or matching placebo administered twice a day for 85 consecutive days (Day 1 to Day 85; the last dose of IMP is taken by subject on Day 85 as the morning dose). Study visits are calculated from Visit 2 Baseline/Day 1/Week 0. All visits should take place as close to the scheduled visit day as possible. In case of unpredictable events (participant hospitalization, the site closure, etc.) which can have an impact on scheduled visit a new visit day should be scheduled or re-scheduled as close to the original visit date as possible.

[figure not shown]

Fig. 4. Dosing sequence scheme during the day. CPL409116 oral administration.

During the treatment period apart from the IMP administration patients are to administer methotrexate (MTX) as a continuation of the background RA therapy. MTX must be administered for at least 12 weeks prior to Screening, and with no change in dosage and route of administration for at least 8 weeks prior to Day 1/ Baseline. The MTX dosage at Baseline (ranged from 15-25 mg/week, which is typical of current Polish practice) and route of administration is to remain stable during the study. A lower dose of  $\geq 10$  mg/week is acceptable if reduced for reasons of side effects or intolerance to MTX, e.g. nausea/vomiting, hepatic or hematologic toxicity (there must be clear documentation in the medical record).

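### SAP 4.2.6 counts a vomited dose as compliant, contrary to protocol 6.7, scores early withdrawals against 169 planned doses, and gives two units for total exposure

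*SAP*

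**What the plan says.** SAP 4.2.6 defines adherence from the patient diary as compliant doses divided by doses to be taken. Three parts of that section matter here.

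- **Denominator and threshold.** "Number of doses to be taken is equal to 169 (84 days * 2 + 1"). There is no rule for patients who stop early. The threshold is "A patients is to be considered as a complier with dosing regimen when at least 80% of the doses are compliant (136 doses"). Protocol 6.7 sets the same fixed count: "at least 80 % of the doses are compliant (at least 136 doses").
- **Compliant dose.** The SAP says: "A single dose is to be consider as a compliant when all 4 tablets are administered". Protocol 6.7 has the 4-tablet condition and a second one, that "administration is without any emesis occurring within 2 hours after IMP administration". The SAP omits the second without giving a reason, although its introduction says that it reflects protocol version 3.0.
- **Exposure unit.** The total over patients is to be "expressed in patient-treatment years", but the formula beneath reads "Extent of exposure [patient months] = sum(Exposure)/30.44".

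SAP 4.17 presents exposure and adherence in tables with descriptive statistics.

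**The concern.** The two documents give different answers to whether a given dose was compliant. Protocol 6.9 tells patients not to replace a dose vomited at home, so such a dose is not made up later, yet the SAP counts it in full. Protocol 7.2 has its own withdrawal rule for emesis, so the event is foreseen.

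The denominator raises a separate problem. Under protocol 7.2 a patient who stops treatment leaves the trial, and some stops have nothing to do with tablet-taking; a positive SARS-CoV-2 test, for example, ends dosing (Table 1, footnote x). For these patients 169 is not the number of doses that were due. A low percentage may then mean missed tablets or an early exit, and the table cannot show which.

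What is at stake is how the adherence and exposure tables read beside the tolerability and exposure-response objectives. A reader could also take patient-months for patient-years.

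**Working it through.** **Inputs.** Two doses a day on Days 1 to 84 and one on Day 85, since "the last dose of IMP is taken by subject on Day 85 as the morning dose" (protocol 4.1); 80% threshold (protocol 6.7, SAP 4.2.6); divisor 30.44 (SAP 4.2.6); 16% drop-out of about 100 patients (protocol 11.2, SAP 2.3).

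**1. The plan's own figures.** 84 × 2 + 1 = 169. 0.80 × 169 = 135.2, so at least 136 doses are needed. Both figures reproduce.

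**2. Emesis condition.** Take a patient who takes all 169 doses and vomits *v* of them within 2 hours. The SAP score is 169/169 = 100% for any *v*. The protocol score is (169 − *v*)/169.

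- *v* = 10: 159/169 = 94.1%, complier under both documents.
- *v* = 33: 136/169 = 80.5%, complier under both.
- *v* = 34: 135/169 = 79.9%, complier under the SAP only.

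Each such dose raises the SAP score by 1/169 = 0.6 points. The documents give no emesis rate, so the number of patients affected cannot be stated.

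**3. Fixed denominator.** With perfect intake, doses taken through the morning of Day *d* number 2(*d* − 1) + 1.

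| Last dose taken | Doses | Share of 169 | Complier |
|---|---|---|---|
| Day 43 morning | 85 | 50.3% | no |
| Day 57 morning | 113 | 66.9% | no |
| Day 68 morning | 135 | 79.9% | no |
| Day 68 evening | 136 | 80.5% | yes |
| Day 84 evening | 168 | 99.4% | yes |

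Against the doses due up to the last dose, every row would read 100%.

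**4. Effect on the overall table.** The documents do not say when drop-outs occur, so timing is assumed. Take 16% withdrawing and perfect intake in everyone while on treatment.

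- Withdrawals uniform over time: mean adherence is about 0.16 × 0.5 = 0.08, or 8 points, too low, and about 0.16 × 68/85 = 12.8% of patients cannot be compliers.
- All withdrawals right after the first dose: 0.16 × 168/169 = 15.9 points, and 16% cannot be compliers.
- All withdrawals at the Day 68 evening dose or later: at most 0.16 × 33/169 = 3.1 points, and none is forced to be a non-complier.

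**5. Exposure unit.** 365.25/30.44 = 12.0. As an illustration, 100 patients with 85 days each give 8500/30.44 = 279.2 patient-months, which is 8500/365.25 = 23.3 patient-years.

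**The case against.** The strongest reply on the denominator is that both documents define a complier relative to the planned regimen. The share of planned doses received is a legitimate measure, and the 136-dose count comes from the protocol. An on-treatment measure has a fault of its own: protocol 7.2 withdraws patients who do not follow the treatment schedule, and ending their denominator at withdrawal can raise their score. Early terminations are also shown by study month (SAP 4.7), exposure is tabulated next to adherence (SAP 4.17), and vomiting reported as an adverse event is tabulated. A careful reader can separate part of the effect.

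Most of this stands. It is why both measures should be shown and why the point is limited to descriptive tables. It does not answer the emesis discrepancy, which affects patients who complete treatment as well as those who withdraw.

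A further fair objection concerns data. Adherence rests on the diary, for which protocol 6.7 describes dosing times, and adverse event times are recorded only when known (protocol 8.1). Timing of emesis within 2 hours of a home dose may not be captured. That has to be confirmed before the SAP is changed.

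A reader might infer more than the documents support:

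- *That every early withdrawal becomes a non-complier.* Only those who stop before the Day 68 evening dose are forced to.
- *That the exposure formula is wrong.* Dividing by 30.44 is right for months; only the sentence above it conflicts.
- *That the arms will differ by a known amount.* The documents give one overall drop-out rate and none by arm.
- *That the per-protocol set or the efficacy result is distorted.* The per-protocol set already requires completion of Day 85 (SAP 3.1), and the deviation for substantial dosing departures (SAP 3.3) is not tied to the 80% rule.

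**Conclusion.** The point holds, within limits. The SAP's compliant-dose definition contradicts protocol 6.7, and for a patient who takes every dose, 34 doses vomited within 2 hours are enough to change the complier label. The fixed denominator, whose 136-dose threshold the two documents share, makes complier status unattainable for anyone stopping before the Day 68 evening dose. Under the planned 16% drop-out with uniform timing, it lowers mean adherence by about 8 points; other timings give anything from under 1 to about 16. The two exposure labels differ 12-fold, and a reported total would be misread by that factor only if the years label were kept.

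The dose counts and the unit ratio follow from the documents alone. The 8-point figure rests on the assumed timing and on perfect intake while on treatment. Nothing here reaches the primary analysis.

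**What to change.** 1. Confirm whether emesis within 2 hours of a dose can be derived from the diary, dosing records and adverse event times. Then reconcile the compliant-dose definition in SAP 4.2.6 with protocol 6.7. If the timing cannot be derived, say so in the SAP and justify the departure.
2. Report adherence against doses scheduled from the first dose to discontinuation or Day 85, whichever comes first. Keep the protocol's 136-of-169 complier flag beside it, or amend both documents together; changing the SAP alone would open a new discrepancy with protocol 6.7.
3. Use one exposure unit: months with 30.44 or years with 365.25, with matching text.

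The cost is SAP wording, minor programming and one more table column. The downside is that on-treatment adherence can look better for patients withdrawn for non-compliance, so neither measure should be shown alone.
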